7.3 LOST TO FOLLOW-UP

A participant will be considered lost to follow-up if he or she fails to return for the final, 12-month follow-up assessment. If a participant misses intervention calls or follow-up assessments prior to the 12-month time point and cannot be contacted during the time frame, the study team will still attempt to contact the participant for remaining calls / assessments. The study team must attempt to contact a participant at least 3 times, on different days of the week, different times of day, and across at least 2 weeks, before they are considered to have missed a visit / assessment or be lost to follow-up. These contact attempts will be documented in the study database.

8 STUDY ASSESSMENTS AND PROCEDURES

8.1 ENDPOINT AND OTHER NON-SAFETY ASSESSMENTS

Measures will be collected at baseline, 6-months and 12-months by a trained study team member blinded to randomization assignment. Measures will be administered in-person at baseline and 12-months and at 6-months via phone. We may schedule a time to call the participant before or after the in-person 12-month visit to complete the questionnaires over the phone. Participants will be paid \$60 for baseline and 12-month assessments (\$45 for in-person visits + \$15 to wear and return the accelerometer) and \$40 for 6-month assessments (\$25 for phone-based assessments + \$15 to wear and return the accelerometer).

Feasibility Metrics. We will compute the proportion of patients who are eligible and who consent to participate in the study, mean number of intervention visits attended, and proportion of participants who complete follow-up assessments. We will also determine the proportions of participants who meet criteria for and are interested in each type of additional intervention (at 6-month follow-up), and we will track participants' use of these services during the study period.

Acceptability of OA CARE. We will ask all participants in the OA CARE group to complete a series of satisfaction ratings and open-ended questions regarding different components of the intervention. We will not collect formal measures from referring PCPs. However, following the completion of the study, we will contact providers and ask for their suggestions on ways in which OA CARE could be improved. This will be approached as a stakeholder engagement type of activity, and PCPs will not be considered research participants for this purpose.

Primary Patient Outcome: Western Ontario and McMaster Universities Osteoarthritis Index (WOMAC). The primary outcome for this study is the WOMAC, a measure of lower extremity pain (5 items), stiffness (2 items), and function (17 items). All items are rated on a Likert scale of 0 (no symptoms) to 4 (extreme symptoms). The

WOMAC has well established psychometric properties including reliability, construct validity and internal consistency ⁵⁴. The WOMAC has been widely used in trials of behavioral interventions for patients with lower extremity OA, confirming its sensitivity to change in this context. In addition to the total WOMAC score (primary outcome), we will separately examine WOMAC pain and function subscales.

Secondary Patient Outcomes.

Body Weight. We will assess body weight using a research / clinical grade scale (e.g., Tanita) that will be calibrated regularly. We will also measure participants' height in order to calculate body mass index.

Physical Activity. All participants will be asked to wear an Actigraph GT3X+ (Pensacola, FL) ⁵⁵at the hip during waking hours for 7 days. We will use data processing and logistical methods we have used successfully in prior work ³³. Physical activity metrics will include minutes of any intensity activity (primary), minutes of moderate to vigorous intensity physical activity, step counts and sedentary time. We will also ask participants to complete a modified version of the Community Health Activities Model Program for Seniors Physical Activity Measure ⁵⁶, which provides information on the types of activities in which participants are engaging.

Physical Function. We will administer tests recommended by the Osteoarthritis Research Society International for clinical trials of knee OA including a 30-second chair stand test and timed up-and-go test ⁵⁷. We will also include a 2-minute march test as an assessment of endurance ⁵⁸ These tests will be conducted in accordance with established protocols ^{57,58}.

Exploratory Patient Outcomes.

Sleep Measures. Sleep apnea symptoms will be assessed with the STOP Questionnaire ⁵², and insomnia symptoms will be assessed with the Insomnia Severity Index ⁵³. These measures were selected based on clinical practice guidelines ⁵⁹.

Psychological Measures. We will assess depressive symptoms via the Patient Health Questionnaire-8 (8-item measure, higher ⁶⁰, the Pain Catastrophizing Scale ⁶¹, and the Arthritis Self-Efficacy Scale ^{62,63}. These are all validated scales used widely in the context of OA trials.

Balance. We will assess balance with a single leg stance test, using established protocols ⁵⁸. The maximum possible standing time will be 30 seconds, and we will also designate whether participants achieve a commonly utilized threshold of 10 seconds.

Participant Characteristics. We will collect the following information to characterize the study sample: age, race / ethnicity, sex, education level, work status, household income, health insurance status, marital status, comorbid illnesses ⁶⁴, joints with arthritis symptoms, and duration of knee / hip OA symptoms.

Costs. Although costs are not a primary focus of this exploratory trial, we will collect these data to refine processes for the larger trial. This will include costs of the YMCA Medical Membership, costs (to both the health system and patients) associated with additional clinical services that result from 6-month screening and referrals, and patients' self-reported costs for engaging any additional community-based services or programs.

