1.2 SCHEMA

1.3 SCHEDULE OF ACTIVITIES

		Pre-screening (Pre-consent)	Visit 1 Day 1	Visit 2 Day 11 to 25	Visit 3 (1 to 2 weeks after Visit 2)	Visit 4 (1 to 2 weeks after Visit 3)	Visit 5 (5-6 months after Visit 2)	Visit 6 (OA CARE 6 Months after Visit 2; Usual Care 6-months after Visit 2)	Visit 7 (OA CARE 12-months after Visit 2; Usual Care 12-months after Visit 2)
EMR Review Eligibility	X								
Screening Phone Call									
Informed Consent & HIPAA	X								
Outcome Measures									
Objectively Assessed Physical Activity (accelerometer)	X						X	X	X
Patient Reported Measures:									
-Physical Function (WOMAC)	X						X	X	X
-Pain (WOMAC)	X						X	X	X
-Sleep (STOP Questionnaire and Insomnia Severity Index)						X	X	X	X
-Psychological Measures (Patient Health Questionnaire-8, Pain Catastrophizing Scale and Arthritis Self-Efficacy Scale)						X	X	X	X
-Modified version of the Community Health Activities Model Program for Seniors (CHAMPS) Physical Activity Measure	X					X	X	X	X
BMI measure							X	X	X
Physical Performance Measures:							X	X	X
-30-second stair stand test	X						X	X	X
-Timed up-and-go test	X						X	X	X
-2-minute march test	X						X	X	X
-Single Leg Stance Test	X						X	X	X
Participant Characteristics	X						X	X	X
Acceptability							X	X	X
Randomization		X							
Control & Experimental Interventions:									
-OA CARE			X	X	X	X	X	X	X
-Usual Care Control			X	X	X	X	X	X	X
Adverse Event Reporting			X	X	X	X	X	X	X

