7 STUDY INTERVENTION/ DISCONTINUATION AND PARTICIPANT DISCONTINUATION/WITHDRAWAL

7.1 DISCONTINUATION OF STUDY INTERVENTION

When a participant discontinues the *OA CARE* intervention, they will be asked if they are willing to continue with other remaining activities (e.g., follow-up assessments) based on the study protocol. If a clinically significant finding is identified after enrollment (e.g. health-related changes that may change the safety level of participation), the investigator or qualified designee will determine if any change in participant management is needed. Any new clinically relevant finding will be reported as an adverse event (AE). The data to be collected at the time of study intervention discontinuation will include the reason(s) for discontinuing the participant from the intervention, and methods for determining the need to discontinue.

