7.2 PARTICIPANT DISCONTINUATION/WITHDRAWAL FROM THE STUDY

Participants are free to withdraw from participation in the study at any time upon request. An investigator may discontinue a participant from the study for the following reasons:

- Lost-to-follow up; unable to contact subject
- Any event or medical condition or situation occurs such that continued collection of follow-up study data would not be in the best interest of the participant or might require an additional treatment that would confound the interpretation of the study
- The participant meets an exclusion criterion (either newly developed or not previously recognized) that precludes further study participation

The reason for participant discontinuation or withdrawal from the study will be recorded in the study database. Participants who discontinue or are withdrawn will be replaced up to the point of randomization assignment being given to the participant. Once participants are given their randomization assignment, they will be counted toward the total study sample size and not replaced.

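### Participants who leave the study before about 6 months have no planned satisfaction rating, so the acceptability summary may rest mainly on those retained

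*Combined protocol and SAP*

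**What the plan says.** Section 3 of the protocol lists acceptability, with feasibility, under the primary objectives and treats these metrics as needed to judge whether a larger trial can be run. Section 8.1 states the intention for patients: "We will ask all participants in the OA CARE group to complete a series of satisfaction ratings and open-ended questions". That sentence names no time point. The same section opens with the general rule "Measures will be collected at baseline, 6-months and 12-months by a trained study team member blinded to randomization assignment".

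The Schedule of Activities (Section 1.3) has the row "Acceptability X X X", with its marks in the last three columns. The first of these is headed "Visit 5 (5-6 months after Visit 2"). There is no column for an exit or early-withdrawal contact.

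For someone who stops the intervention, Section 7.1 says "they will be asked if they are willing to continue with other remaining activities (e.g., follow-up assessments"), and the data taken at that point "will include the reason(s) for discontinuing the participant from the intervention, and methods for determining the need to discontinue". For someone who leaves the study, Section 7.2 says "The reason for participant discontinuation or withdrawal from the study will be recorded in the study database". Neither section mentions a rating. Section 7.3 requires repeated contact attempts and continued attempts at later assessments after one is missed.

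Section 9.4 summarises the acceptability metrics descriptively with 95% confidence intervals. It gives no denominator and no rule for missing ratings.

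**The concern.** The stated intention covers everyone in the OA CARE arm, but the procedures do not deliver it for those who leave early. The component that every OA CARE participant starts with is a weight loss program of 12 weekly sessions (Section 6.1). A person can begin it, dislike it and withdraw from the study well before the first scheduled rating. Section 9.2 expects some drop-out, and Section 7.2 does not replace anyone who has been told their assignment.

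If withdrawal is related to how participants found the program, the ratings that are missing differ from those received. A confidence interval computed among raters describes sampling error only and says nothing about who is missing. The provisions for missing data in Section 9.4 are written for the outcome models and are not extended to acceptability. The recorded reasons help, but they are not ratings of the separate intervention components, which is what a redesign would draw on.

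**Working it through.** The plan gives no acceptability figure to reproduce, so the check has two parts.

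**1. When can a rating first be taken?**

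- Section 8.1, ratings sentence: all OA CARE participants, no time given.
- Section 8.1, general rule: baseline, 6 and 12 months. Baseline precedes the intervention, so the first usable point is 6 months.
- Section 1.3: Visits 5, 6 and 7, so from 5 to 6 months after Visit 2. The columns of this table may have shifted in the available copy. It marks performance tests at all three of these visits, while Sections 3 and 4.1 place them at baseline and 12 months only. The conclusion does not depend on the table, because the text of Section 8.1 gives about the same first time point.
- Sections 7.1 and 7.2: reasons, and in 7.1 also how the need to discontinue was determined. No rating is listed.

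| Participant | Planned rating? |
|---|---|
| Stops OA CARE, stays in follow-up | Yes, at follow-up |
| Leaves the study after Visit 5 or 6 | May already have rated |
| Leaves the study before Visit 5 | None described |

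The gap is confined to the last row, together with people lost to contact before any rating.

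**2. How much could it matter?**

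Inputs: 60 participants randomised equally (Section 4.1), so n = 30 in OA CARE. The plan states no drop-out rate and defines no satisfied proportion, so both are assumed here. Let m be the number unrated and s the number satisfied among the n − m raters.

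- Observed proportion = s / (n − m)
- Lowest possible value for all randomised = s / n
- Highest possible value = (s + m) / n
- Width of the range = m / n, whatever s is

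Main illustration, m = 6 and s = 20:

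- Observed 20/24 = 83.3%
- Lowest 20/30 = 66.7%
- Highest (20 + 6)/30 = 26/30 = 86.7%
- Width 6/30 = 20 percentage points

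Range over assumed loss, with about 80% of raters satisfied:

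| Unrated | Raters satisfied | Observed | Bounds for all 30 | Width |
|---|---|---|---|---|
| 3 (10%) | 22/27 | 81.5% | 73.3% to 83.3% | 10 points |
| 6 (20%) | 19/24 | 79.2% | 63.3% to 83.3% | 20 points |
| 9 (30%) | 17/21 | 81.0% | 56.7% to 86.7% | 30 points |

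For scale, the Wilson 95% interval for 20/24 has centre (0.8333 + 3.8416/48)/(1 + 3.8416/24) = 0.787. Its half-width is 1.96 × √(0.8333 × 0.1667/24 + 3.8416/2304)/1.160 = 0.146, so it runs from about 64% to 93%. That interval measures sampling error among raters. The bounds measure what is unknown about the 30 people actually randomised, and one does not stand in for the other.

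**The case against.** The strongest reply is that the plan is less exposed than it looks. Section 8.1 says all OA CARE participants will be asked and does not confine asking to visits. Stopping the intervention is not leaving the study: Section 7.1 invites discontinuers to stay in follow-up, Section 7.3 chases missed assessments, and the 6-month assessment is by phone and paid. Reasons for leaving, visits attended and follow-up completion are all recorded. Aim 1 has no hypothesis (Section 9.1), and no acceptability threshold decides whether a larger trial proceeds.

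Most of this stands, and it narrows the point to study withdrawal or loss before the first rating. It does not close the gap, because no passage says how or when such a person would be asked.

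A reader might go further and infer that early leavers are never asked, that only completers are rated, or that the result is biased upward by a known amount. The documents support none of these. The first is an inference from silence. The second conflicts with ratings being scheduled from Visit 5, since completion means the 12-month assessment (Section 4.4). The third needs the leavers' views, which are unknown; Section 7.2 also lists medical conditions and newly met exclusion criteria as reasons for leaving, and these need not reflect dislike of the program. Nor does Section 9.4 prescribe a responder-only analysis. It leaves the denominator open.

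**Conclusion.** The concern holds in limited form. The plan intends ratings from everyone in OA CARE but describes none for a participant who leaves the study before about 5 to 6 months, and it does not say how missing ratings enter the summary. The estimate may therefore rest mainly on people retained to about 6 months.

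The uncertainty this adds, in percentage points, equals the percentage of the arm left unrated: 10 to 30 points if 3 to 9 of 30 are unrated, and 67% to 87% in the main illustration. Those counts are assumptions, and the direction of any bias cannot be determined from the documents. This does not threaten the trial's validity, but it bears on a primary objective and is easily repaired before data collection ends.

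**What to change.** - **Section 7.2:** add the same short satisfaction ratings and open-ended questions, voluntary, to the withdrawal contact. Do the same in Section 7.1 for anyone who stops the intervention and declines further follow-up.
- **Who asks:** an unblinded coordinator. The Navigator should not collect ratings of their own service, and a blinded outcome assessor would learn the assignment by asking.
- **Sections 8.1 and 1.3:** state when ratings are taken, including at withdrawal.
- **Section 9.4:** report acceptability among responders, the number rated out of all randomised to OA CARE, and best- and worst-case bounds for the unrated. State in advance which rating counts as satisfied so that the bounds can be computed.

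Satisfied participants over all randomised should not be the sole headline. It counts everyone who could not be reached as dissatisfied, so it is the worst-case bound (20/30 in the illustration) and should be labelled as such.

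The cost is a few extra questions at the withdrawal contact. People who cannot be contacted will still be missing, which is why the bounds are needed as well as the exit questions.

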8.2 SAFETY ASSESSMENTS

If a study team member learns of any adverse events (AEs) that occur in the course of participants' home exercise, this will be documented on the Adverse Events form, as described below.

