2.2 RISK/BENEFIT ASSESSMENT

2.2.1 KNOWN POTENTIAL RISKS

Emotional distress: it is unlikely that the types of questions participants will be asked in this study will result in emotional distress, but we understand that participants may be uncomfortable with answering questions about some aspect of their health or other things about them. To minimize this risk, we will let participants

know they may choose not to answer any study questions and can still be involved in the study. Additionally, participants in the *OA CARE* intervention will have contact information for the study team (e.g. *OA CARE* Navigator) and a YMCA health coach to discuss any concerns.

Breach of confidentiality: we will be collecting some elements of personal health information necessary for the study. To minimize breaches of confidentiality, all data will be stored on a secure UNC server or a UNC IRB approved platform for sharing PHI (with YMCA) and paper information will be stored in locked filing cabinets in the office of a study team member, and only approved study personnel will have access to those data.

Personal health information (e.g. patient name and contact information only) will be shared with YMCA health coaches and personnel conducting the YMCA weight loss and exercise programs. Any information shared between approved UNC study team members and YMCA personnel will be done verbally by phone, by encrypted email or a UNC IRB approved platform for sharing PHI.

For participants in the *OA CARE* intervention, personal health information (e.g. patient name and DOB or MRN) will be shared with the participant's PCP, as part of the brief progress reports sent by the *OA CARE* Navigator. Any information shared between approved UNC study team members (e.g. *OA CARE* Navigator) and the participant's PCP will be done by encrypted email or UNC IRB approved platform for sharing PHI.

Risks of Exercise: Participants in the *OA CARE* intervention will be involved in physical activity programming at the YMCA. This will be tailored to individuals with knee OA. However, exercise programs may be associated with risk of injury, muscle soreness, and joint pain. The risk of sudden death during physical activity is about 1 death per 656,000 hours of physical activity. In general, the risk of these events with moderate physical activity is very low.

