Weight Loss & Exercise Interventions. Evidence-based weight loss and exercise programs will be delivered by the Triangle YMCA, within the structure of the Medical Membership. (All services provided to study participants by the YMCA will be their standard programming; they will note be delivering a study-specific intervention.) This membership provides access to multiple group exercise programs, exercise facilities, and a health coach who assists members with meeting health goals and selecting appropriate programs and classes. All patients in OA CARE will begin with participation in the YMCA’s Weight Loss Program (Program). This program involves 12 weekly sessions that include goal-setting, food and activity tracking, introduction to physical activity offerings, and weigh-ins. This Program is based on best practices from evidence-based behavioral weight loss programs. Participants may repeat the program following the first 12-week session if they have not met weight loss goals and / or would like continued structure and support for these behavior changes. The Triangle YMCA will deliver the Weight Loss Program to OA CARE members in groups of approximately 10; this will provide cohesion for OA CARE participants. In the beginning of the study, the Program will be delivered virtually (e.g. video conferencing platform) for feasibility reasons (e.g., potential for study participants to reside in different geographic locations that would make travel to a central location challenging). However, the Program may be offered in-person in the future. During the screening call, we will assess whether the patient has internet access and a device (computer, tablet, smartphone) on which they can access the Program. If the patient screens ineligible for this reason, we will ask the patient if they would like to be contacted, if the Program is offered in-person at a future date. If we do offer the Program in person, this will no longer be considered an exclusion criterion. The YMCA offers many exercise programs and classes appropriate for individuals with OA. A YMCA health coach will assist participants with selecting an exercise program (including appropriateness based on their pain and functional limitations) and continuing to engage with exercise-based therapies throughout their 12-month involvement in OA CARE. The UNC study team will also give participants instructions regarding how to access a free Walk With Ease workbook (through the OAAA’s online portal) and take advantage of other tools available through this program.

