
Version 4.0

[figure not shown]

Figure 2. OA CARE Intervention

Additional Tailored Services. After 6-months, we will administer a series of questionnaires to assess patients' needs for and interest in additional interventions included in OA treatment guidelines (Table 1) ^{10,20}. Our multidisciplinary study team, which includes individuals with deep expertise in OA treatment and guidelines, has developed algorithms to guide these referrals. Patients will be given information on the types of interventions shown in Table 1 (via mail or email), and the OA CARE Navigator will engage patients in a shared decision-making process (via phone) regarding additional referrals, with a focus on interventions for which they meet criteria shown in Table 1. However, the OA CARE Navigator will facilitate referrals and recommendations for any services of interest to patients, regardless of criteria shown in the table. Any referrals for clinically-based services (e.g., physical therapy, sleep testing) will be coordinated with the PCP. Table 1 also shows examples of interventions and resources within each category, ranging from free, publicly available programs to individual clinical services; some services will be relevant regardless of geographic location and some will be customized based on local resources, as we have done previously ³³. The OA CARE Navigator will also call participants about a month later to follow up on any questions they may have regarding resources or referrals. The OA CARE Navigator may also conduct additional calls with a participant if needed to coordinate connection with resources or referrals.

Table 1. Criteria and Examples of Additional Tailored Services

Type of Service	Criteria	Example Interventions & Resources
Psychological Interventions	Subgroups for Targeted Treatment (STarT Back) Tool ⁴⁷⁻⁴⁹ : 4 or more psychosocial risk factors (pain bothersomeness, fear, worry, catastrophizing, depression) ⁵⁰	Free, evidence-based pain coping skills training programs (e.g. painTRAINER) and referral to local mental health providers who specialize in pain management
Physical Therapy	Persistent self-reported difficulty with walking or stair-climbing, balance difficulties, recent falls or pain as a limitation to engaging in regular exercise	Referrals based on patients' preferences for location, geography, and health insurance coverage

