6.4 STUDY INTERVENTION ADHERENCE

The study database will be used to track participants' completion of all assessment visits, as well as all contacts with the *OA CARE* Navigator. The coordinator will also maintain close communication with the *OA CARE* Navigator regarding facilitation of all activities within the care pathway. The YMCA will provide documentation of patients' participation in specific YMCA programs to the *OA CARE* Navigator; this information will also be summarized for PCPs. Also, for each patient, the *OA CARE* Navigator will maintain a checklist of intervention activities, target dates, dates of completion, and comments.

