8.3.4 TIME PERIOD AND FREQUENCY FOR EVENT ASSESSMENT AND FOLLOW-UP

The occurrence of an AE or serious adverse event (SAE) may come to the attention of study team members during study visits. All AEs, not otherwise precluded per the protocol, will be captured on the Adverse Event Form. Information to be collected includes event description, time of onset, PI or co-investigator's assessment of severity, relationship to study procedures (assessed only by those with the training and authority to make a diagnosis), and time of resolution/stabilization of the event. All AEs occurring while on study will be documented appropriately regardless of relationship. All AEs will be followed to adequate resolution.

Any medical or psychiatric condition that is present at the time that the participant is screened will be considered as baseline and not reported as an AE. However, if the study participant's condition deteriorates at any time during the study, it will be recorded as an AE.

Changes in the severity of an AE will be documented to allow an assessment of the duration of the event at each level of severity to be performed. Documentation of onset and duration of each episode will be maintained for AEs characterized as intermittent.

The Project Coordinator will record events with start dates occurring any time after informed consent is obtained until 7 (for non-serious AEs) or 30 days (for SAEs) after the last day of study participation.

Participants are identified in the EMR as a study participant and for each AE/SAE occurrence, research team members will receive an alert through EMR. AEs or SAEs may also be reported to study physical therapist during the course of intervention visits. Events will be followed for outcome information until resolution or stabilization.

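### The safety sections describe home exercise and a study physical therapist rather than the YMCA-delivered intervention, so non-serious events outside the EMR may be missed and counts by arm may not be comparable

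*Combined protocol and SAP*

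**What the plan says.** Section 8.2 is one sentence. It applies when a study team member hears of an event in participants' "home exercise, this will be documented on the Adverse Events form", and it then points to the rules that follow.

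Section 8.3.4 gives three routes. Events "may come to the attention of study team members during study visits". Participants are flagged in the EMR, which alerts the team to events. Finally, "AEs or SAEs may also be reported to study physical therapist during the course of intervention visits". The same section requires every on-study event to be documented whether or not it is related. The recording window runs from consent to 7 days (non-serious) or 30 days (serious) after participation ends. The Schedule of Activities (Section 1.3) has one AE row, not split by arm.

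On delivery, Section 6.1 states: "Evidence-based weight loss and exercise programs will be delivered by the Triangle YMCA". Physical therapy appears there only in Table 1, as a service offered after the 6-month screen: "Referrals based on patients' preferences for location, geography, and health insurance coverage". Under Section 6.4 the YMCA documents "participation in specific YMCA programs to the" Navigator; AEs are not mentioned. Section 2.2.1 accepts that "exercise programs may be associated with risk of injury, muscle soreness, and joint pain", and lists fainting or light-headedness among the weight-loss risks. It gives OA CARE participants two people to turn to, the Navigator and "a YMCA health coach to discuss any concerns", but does not ask the coach to pass anything on.

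**The concern.** The setting and the role named in the safety sections are not those of the intervention. An exercise class or a weight-loss session is outside the literal wording of Section 8.2, and the therapist named as a recipient of reports has no place in the delivery described in Section 6. The YMCA staff who run the programmes are not named as a source.

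Two things are at stake. The first is completeness: a strain in a class, or a brief faint that needs no medical visit, may never reach the study. There is no data safety monitoring board, and the Safety Officer works from twice-yearly reports prepared by the investigator (Section 10.1.6), so oversight is only as complete as capture. The second is comparability: where capture depends on an event happening to be mentioned, the arm that speaks to the team more often has more chances to mention one. A pilot meant to prepare a larger trial should also show that its safety route works.

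**Working it through.** The plan gives no figure to reproduce. The check compares the text and counts contacts.

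**Text comparison**

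| Element | Safety sections | Intervention sections |
|---|---|---|
| Setting of the event | Home exercise (8.2) | YMCA weight-loss and exercise programmes (6.1); some self-directed exercise through the Walk With Ease workbook (6.1) |
| Who may receive a report | Study team at study visits; EMR alert; study physical therapist (8.3.4) | Navigator, YMCA coach and class staff, PCP; physical therapy by outside referral after 6 months (6.1) |
| What the YMCA passes on | Not addressed (8.2, 8.3.4) | Participation records only (6.4) |
| Standard AE question put to both arms | None described | None described |

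The EMR route covers both arms. I assume that it can signal only what is entered in that system. What remains exposed is the non-serious event that leads to no record there.

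**Planned study-team contacts after randomization**

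- Usual care: the 6-month and 12-month assessments (Section 8.1), so k = 2.
- OA CARE: the same two, plus the Navigator's 6-month call and the call about a month later (Section 6.1), so k = 2 + 2 = 4 at least. Further Navigator calls are optional.
- The 12 weekly YMCA sessions are left out, because nothing written carries an event from them to the study.

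**Illustration**

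Let q be the chance that an event is mentioned and recorded at any one contact, equal in both arms and independent across contacts. The documents do not give q, so a range is assumed. The chance of capture over k contacts is 1 − (1 − q)^k. The ratio of 4 contacts to 2 is then 1 + (1 − q)².

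| Assumed q | Usual care, k = 2 | OA CARE, k = 4 | Ratio |
|---|---|---|---|
| 0.1 | 19% | 34% | 1.81 |
| 0.2 | 36% | 59% | 1.64 |
| 0.3 | 51% | 76% | 1.49 |
| 0.5 | 75% | 94% | 1.25 |

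These ratios apply to events before the 6-month contacts. After the last planned Navigator call, each arm has only the 12-month assessment left, and the ratio is 1. EMR alerts would narrow the gap for any event that reaches the EMR.

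**The case against.** The strongest reply is that this is loose wording around a sound general rule. Section 8.2 does not restrict recording to home exercise; it names that setting and defers to Section 8.3, where all events must be documented. Study-visit capture and EMR alerts apply to every participant. Any AE system depends on someone learning of the event. This is a 60-person, minimal-risk pilot with an independent Safety Officer. Most of this stands, and it limits the point to non-serious events outside the EMR.

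Four stronger readings are tempting, and the documents do not support them:

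- *Safety capture as a whole covers only home exercise, or Sections 8.2 and 8.3.4 contradict each other.* Section 8.2 is narrower than 8.3.4 but hands over to it.
- *The trial has no home exercise and no physical therapist.* The Walk With Ease workbook is self-directed, and the exclusion criteria in Section 5.2 mention a home exercise programme. The Key Roles section was not in the text available for review, so one can say only that Section 6 describes no therapist delivering visits.
- *The 12 weekly sessions and the coach inflate OA CARE reporting.* If YMCA contacts have no route to the study, they cannot add reports. The documented excess is two Navigator calls. Nor can YMCA staff be assumed to see weight-loss events first, since that programme begins by video.
- *A planned safety comparison is biased.* Section 9.4 plans no comparison of AEs by arm.

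A further fair objection is that naming YMCA staff as reporters adds a source in one arm only. That is correct, and the reporting has to allow for it.

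**Conclusion.** The point holds in a limited form. The home-exercise and therapist wording does not match the intervention. YMCA staff have no stated duty to forward events, and capture outside the EMR is passive. Serious events are likely to surface under the existing rules; minor ones may not.

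The documented imbalance is four planned study-team contacts against two. The 1.81 to 1.25 ratio shows only what that could do under an assumed q, with equal true rates and no help from the EMR. The net direction is not established: extra Navigator calls raise recorded events in OA CARE, while the missing YMCA route lowers them. The consequence for comparability is conditional. It matters only if AE counts are shown by arm. The broken schedule table and missing schema leave unclear who attends Visits 3 to 5, so the count of two extra contacts rests on Sections 6.1 and 8.1. The change is worth making, and it does not call the design into question.

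**What to change.** 1. Reconcile Sections 6.4, 8.2 and 8.3.4. Word 8.2 to cover all AEs, including those in YMCA activities.
2. In 8.3.4, replace the study physical therapist with the Navigator, or state who holds that role.
3. Add AEs to the information that the YMCA already sends to the Navigator under Section 6.4.
4. Put one identical scripted AE question to both arms at the 6-month and 12-month assessments. Place it after the outcome measures, so that an answer revealing YMCA attendance cannot influence the blinded assessor's ratings at that visit.
5. If AEs are summarised by arm, show the solicited events separately from those found through the EMR, the Navigator or the YMCA. Report all SAEs whatever their source, including those in the 30-day window after participation ends. The solicited events are the like-for-like comparison; the others are still reported in full.

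The cost is wording, one question at two existing contacts and a little more recording work. It also needs agreement with the YMCA on forwarding events, since the YMCA is providing its standard programming. A small unblinding risk remains: an assessor who hears of YMCA attendance at 6 months may also conduct the 12-month visit. Using a different assessor or a self-completed form for the question would reduce it.
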